motor recovery after a stroke. One of these motor-related regions, is the contralateral primary motor cortex (M1) contributes to the motor recovery of the upper extremity after a stroke (**Favre et al, 2014**).

The substantial changes that occur in the cortical reorganization of the brain ischemic areas and of more remote areas play an integral role in the recovery of motor dysfunction post stroke. The injured ischemic motor cortex has a reduced cortical excitability at the acute phase and a suspension of the topographic representation of affected muscles, while the contralateral motor cortex has an increased excitability and an enlarged somatomotor representation. The contralateral cortex exerts a transcallosal interhemispheric inhibition on the ischemic cortex. This results from the imbalance of the physiological reciprocal interhemispheric inhibition of each hemisphere on the other, contributing to worsening of neurological deficit (**Zhang et al , 2017**).

Series of repetitive transcranial magnetic stimulation studies on stroke have been trying to understand the relationship between hemiparetic upper limb motor recovery and cortical reorganization post stroke (**Tang et al , 2015**) . Repetitive transcranial magnetic stimulation (rTMS) is a noninvasive stimulation to induce electrical currents in the brain tissues which can modulate cortical excitability of motor areas and enhance recovery. (**Du et al., 2018**). The application of repetitive transcranial magnetic stimulation depend on multiple parameters, such as stimulus-train length, stimulation frequency, number of pulses delivered, their temporal pattern and the targeted region . All of these parameters may differentially affect the responses of the intended target neurons to rTMS (**Matheson et al., 2016**).

Low-frequency repetitive transcranial magnetic stimulation (LF-rTMS) of the contralesional hemisphere is a safe procedure that suppresses local cortical activity of the non-affected cerebral cortex (**Li et al, 2016**). The primary motor cortex (M1) forms a main part of the motor cortices and contributes to the high order control of motor recovery of the hemiparetic upper limbs in stroke patients. It was assumed that the induced inhibitory effect of LF-rTMS on the non-lesional hemisphere can cause direct increase in the neural activation of the lesional hemisphere which can consequently regain the cortical interhemispheric balance and eventually can produce functional improvement in post-stroke patients with upper limb hemiparesis (**Blesneag et al,2015, Du et al, 2018**).

Statement of the Problem:

- Is there a significant effect of the contralesional low frequency repetitive transcranial magnetic stimulation (LF-rTMS) on cortical excitability modulation and consequently on the upper limb motor performance in stroke patients?
- The recommended minimum number of contralesional low frequency repetitive transcranial magnetic stimulation (LF-rTMS) sessions that can induce significant cortical excitability changes in relation to the conventional therapeutic physical therapy interventions in stroke patients?
- The recommended maximum number of contralesional low frequency repetitive transcranial magnetic stimulation (LF-rTMS) sessions that can induce significant cortical excitability changes before reaching a plateau in relation to the conventional therapeutic physical therapy interventions in stroke patients?

Purpose of the study:

- To assess and analyze the effect of contralesional low frequency repetitive transcranial magnetic stimulation (LF-rTMS) on cortical excitability and consequently its impact on the upper limb motor performance in stroke patients.
- To determine the recommended minimum and maximum number of contralesional low frequency repetitive transcranial magnetic stimulation sessions (LF-rTMS) in conjunction with the conventional physical therapy rehabilitation program that can induce significant impact on cortical excitability by analyzing the sequential rate of change in cortical excitability in response to contralesional (Lf-rTMS) stimulation in stroke patients.

Significance of the study

Stroke is a global disease with high rates of long-term disability. It is estimated that 25% to 74% of the 50 million stroke survivors worldwide require some assistance or are fully dependent on caregivers for activities of daily living (ADL) post stroke. (**Veerbeek et al, 2011**). It affects aspects of a person's physical, emotional, and social life. Although stroke is a lesser cause of disability than heart disease, the population of stroke survivors continues to increase, in part because of a fall in mortality rates. This consequently increases the societal burden because of the monetary load and costs of care applied upon the care givers, in-patient hospitals and family members. Upper limb motor rehabilitation is a priority that can be achieved by adopting a cohesive and multidisciplinary approach toward

clinical management and rehabilitation to minimize long-term stroke-related disability (**Santisteban et al, 2016**).

Upper limb motor impairments post stroke result in reduced functional mobility, motor or sensory dysfunctions as well as problems with balance, coordination, postural control, and walking mechanics resulting in increased financial and social burden of stroke patients and their families. These long-term sensorimotor impairments, is usually due to the patients' incapability to execute movements of the affected arm or hand independently. Impairments of the upper extremity post stroke are usually due to direct damage to the primary motor cortex, the primary somatosensory cortex, secondary sensorimotor cortical areas, subcortical structures, and/or the corticospinal tract (**Raghavan , 2015**).

Research in cortical excitability or cortical plasticity modulations highlighted the significance of such processes in the potential enhancement of motor recovery after cerebrovascular stroke. The modules involved in cortical reorganization post stroke can potentiate the results of clinical rehabilitation of various motor impairments in stroke patients. Non-invasive brain stimulation with inhibitory repetitive transcranial magnetic stimulation (rTMS) of the contralesional hemisphere may aid in relieving a post-stroke interhemispheric excitability imbalance, which could improve functional recovery (**Van et al, 2017**) Abnormal cortical excitability and interhemispheric imbalance in stroke patients assumes that, the increased excitability of the contralesional hemisphere applies excessive interhemispheric inhibition onto ipsilesional cortical hemisphere . This excessive imbalanced inhibition impede the neuroplasticity in these areas and limit the gains in motor recovery that can be achieved through rehabilitation (**Boddington & Reynolds 2017**).

Null Hypothesis:

- There is no significant effect of using contralesional low frequency repetitive transcranial magnetic stimulation (LF-rTMS) on cortical excitability and consequently on the motor performance of the affected upper limb in stroke patients.
- There is no change in the sessional values of cortical excitability in response to contralesional low frequency repetitive transcranial magnetic stimulation (LF-rTMS) thus the recommended minimum and maximum number of LF-rTMS sessions that can show significant changes in cortical excitability cannot be determined in stroke patients.

Delimitations:

This study was delaminated to:-

- Forty hemiparetic stroke patients of both genders who met all the inclusion criteria were recruited in this study from outpatient clinic, Faculty of Physical Therapy and outpatient clinic in the Neurology department, Faculty of Medicine, Cairo University.
- Their age ranged from 50 and 65 years
- All patients experienced single ischemic stroke for at least three months but not exceeded for six months.

- All patients were referred from a neurologist and the diagnosis was confirmed with non-contrast computed tomographic (CT) or magnetic resonance imaging (MRI) scans of the brain.
- The selected patients were randomly assigned into two equal groups (control group (GA) and study group (GB)), The randomization was done by random generator using permuted blocks of different sizes(Randomized Controlled Trial).
- All patients were selected with mild to moderate motor impairment verified according to the national istitutes of health stroke scale (NIHSS) (score 1-15) and modified ashworth scale (MAS) (1 or 1+).
- Fugl-Myer upper extremity assessment scale (FMA-UE) and hand grip dynamometer were used to assess the upper limb motor function for each patient in both groups (before and after treatment).
- Single pulse TMS was used to assess cortical excitability represented in measuring the active motor threshold from the contralesional (CAMT) and the ipsilesional (IAMT) primary motor “hot spot” for each patient in both groups (before and after treatment).
- Single pulse TMS was used to assess the sequential change in cortical excitability represented by the sessional measurement of (CAMT) and (IAMT) for all patients in both groups.
- Patients participated in the study were not informed whether they are in the Control group(GA) or in the Study group(GB) (Single blind study).
- The treatment sessions for all patients in both groups was conducted daily, five times per week for two consecutive weeks.
 - The control group (GA) were treated by a conventional physical therapy upper limb rehabilitation protocol (**Lie et al,2015**).

- The study group (GB) were treated with the conventional physical therapy upper limb rehabilitation protocol in addition to the contralesional low frequency repetitive transcranial magnetic stimulation (LF-rTMS).

Limitations:

An Effort was made to minimize the effect of the possible limitations which are:

1. The psycho-physiological status of the patients; all the patients were interested and motivated during all the sessions.
2. The transportation of all patients from the Outpatient clinic, Faculty of Physical Therapy, Cairo University was comfortable and without any effort or extra load on the patient as much as possible.
3. Each patient was assessed using single pulse TMS at the neurophysiology lab at Kasr El Aini, teaching Hospital, Cairo University, at a time suitable for each patient and without any list of waiting as much as possible.

Basic assumption:

It was assumed that:

- The sample of this study were carefully selected to represent all the subacute stroke population.
- Patient's motivation & cooperation were the same throughout the assessment and treatment procedures for each patient.

- All other factors which may influence the outcomes such as noise, distraction....etc during the assessment and treatment sessions were controlled.
- All risk factors of stroke would be controlled to avoid any recurrent stroke or instability of their medical state like blood pressure, glucose and cholesterol level that was achieved with their physicians.

Data Analysis and Statistical Design:

A- Descriptive statistics:

The mean value and standard deviations for upper limb motor function findings represented in **Fugl-Myer Upper Extremity Scale (FMA-UE)**, **Hand grip dynamometer** and Findings of cortical excitability represented in **Contralesional Active Motor Threshold (cAMT) and Ipsilesional Active Motor Threshold (iAMT)** obtained from MagstimRapid² stimulator system were compared for both groups (Control group (GA) and Study group (GB)).

B- Inferential statistics:

- **Student t Test** was used to compare different numerical variables represented in mean values and standard deviations of the patients **chronological features as Age (in years) and duration since onset of stroke (in months)** between both groups ((GA) and (GB)).
- **Student t Test** for independent samples test was also used to compare different numerical variables represented in mean values and standard deviations that were obtained from MagstimRapid2 stimulator system (

cAMT , iAMT) for cortical excitability and upper limb motor function findings (Fugl-Myer assessment- Upper Extremity (FMA-UE), Hand grip dynamometer) between both groups ((GA) and (GB)) (Pre treatment findings).

- **Chi-square (χ^2) Test** was performed to compare the **categorical data** of the patients' main features as gender, smoking history, within and between groups (control group (GA) and study group (GB)). **Fisher's Exact Test** was used instead when the expected frequency is less than 5.
- **Paired t Test** for independent samples test was used to compare the post to pretreatment change between both groups, represented in the mean values and standard deviations obtained for the recorded post to pretreatment difference in cortical excitability (cAMT , iAMT) and upper limb motor function findings ((FMA-UE), Hand grip dynamometer) .
- The mean values of the **Sequential rate of change in cAMT and iAMT** findings over the 10 therapeutic sessions were assessed by comparing the CAMT and the IAMT mean values of each session in relation to the previous session findings for each patient in both groups
- **Paired t Test** for independent samples test was used to compare the mean sessional values (sequential change) and the mean difference in the sessional rate of change of the **cortical excitability findings** represented by cAMT and iAMT between group control group (GA) and study group (GB).
- The alpha point of 0.05 was used as a level of statistical significance (when P = 0.05 is usually classed as “significant”, P = 0.01 as “highly significant”, and P = 0.001 as “very highly significant”) (**Betty and Jonathan, 2003**).

- All statistical calculations were done using computer program IBM SPSS (Statistical Package for the Social Science; IBM Corp, Armonk, NY, USA) release 22 for Microsoft Windows.

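### One fixed ten-session course shows when an excitability change appears during treatment, but does not by itself give a recommended minimum number of LF-rTMS sessions

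*Combined protocol and SAP*

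**What the plan says.** Under Purpose of the study, the second aim is "To determine the recommended minimum and maximum number of contralesional low frequency repetitive transcranial magnetic stimulation sessions (LF-rTMS"), to be met through sessions "that can induce significant impact on cortical excitability by analyzing the sequential rate of change in cortical excitability". The second and third items in Statement of the Problem ask for the same minimum and maximum, relative to conventional therapy. The second null hypothesis states the converse: with no sessional change, "the recommended minimum and maximum number of LF-rTMS sessions that can show significant changes in cortical excitability cannot be determined in stroke patients".

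Delimitations gives the design:
- Sample: "Forty hemiparetic stroke patients of both genders".
- Allocation: "The selected patients were randomly assigned into two equal groups".
- Schedule: "The treatment sessions for all patients in both groups was conducted daily, five times per week for two consecutive weeks".
- Sessional data: cortical excitability is "represented by the sessional measurement of (CAMT) and (IAMT) for all patients in both groups".

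FMA-UE and grip are taken only before and after treatment.

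Data Analysis and Statistical Design, part B, refers to ten therapeutic sessions. It assesses sequential change by "comparing the CAMT and the IAMT mean values of each session in relation to the previous session findings", and tests sessional values and sessional rates of change between the groups at alpha 0.05. The available text gives no rule for turning these tests into a number of sessions, and no adjustment for testing ten sessions and two thresholds.

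**The concern.** A recommended minimum tells clinicians where they may stop. Nobody in this trial stops early, so for GB patients the number of sessions received and the time since first stimulation rise together. If a GB-GA difference first shows at session k, at most k daily sessions were enough for a change visible that day (k-1 if the reading precedes that day's stimulation, which the text does not say). That does not show that fewer were too few.

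The selection adds a second difficulty. The plan defines the target by significant change and tests each session, so the natural reading is to take the first session with p<0.05. That session can come too late if the effect is delayed or power is low, and too early if it is a false positive. A course length based on it could therefore be too long or too short. This point concerns the minimum only; the maximum is not examined here.

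**Working it through.** **Inputs from the document.** 40 patients in two equal groups, so 20 per arm. Five sessions a week for two weeks gives 5 × 2 = 10 sessions, matching the ten stated in part B. Two thresholds (cAMT, iAMT), alpha 0.05. GB patients assigned fewer than ten sessions: 0.

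**Assumptions.** The available text gives no effect size, SD or between-session correlation, and does not say whether tests are two-sided. Calculations use two-sided independent-samples t tests of GB v GA at each session. Within-patient correlation is compound symmetry 0.5 to 0.9 or AR(1) 0.7 to 0.95 (to 0.9 in step 4), and the cAMT-iAMT correlation is 0 to 0.5 (0.3 in step 4). Simulations use 10,000 trials per setting.

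**1. What the readings can separate.** Take two hypothetical patterns: (a) five sessions are needed and the effect is immediate; (b) three are needed and the effect shows two session-days later. On this schedule both give the GB-GA profile 0, 0, 0, 0, 1, 1, 1, 1, 1, 1. No analysis of these readings can tell them apart. Separating them needs patients who stop at three.

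**2. No LF-rTMS effect: chance of at least one p<0.05, 20 per arm.**

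| Looks | Correlated (simulated) | Independent |
|---|---|---|
| First 5 sessions, one threshold | 0.10-0.19 | 1 − 0.95^5 = 0.226 |
| 10 sessions, one threshold | 0.13-0.31 | 1 − 0.95^10 = 0.401 |
| 10 sessions, both thresholds | 0.22-0.52 | 1 − 0.95^20 = 0.642 |

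Holm over the 20 tests brings the last row to 0.02-0.04. If the nine session-to-session change tests per threshold may also pick the session, the unadjusted chance is 0.62-0.77.

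**3. Dependence on sample size.** Assume the difference grows by 0.1 SD per session from session 1. Approximate power at session k with n per arm is Φ(0.1k·√(n/2) − 1.96).
- n = 20: k = 6 gives Φ(1.897 − 1.96) = 0.48; k = 7 gives Φ(2.214 − 1.96) = 0.60.
- n = 40: k = 4 gives 0.43; k = 5 gives 0.61.
- n = 80: k = 3 gives 0.48; k = 4 gives 0.72.

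The first session with at least 50% power is therefore 7, 5 and 4. The simulated median first significant session is about 6 (5 to 7 across correlations), 4-5 and 3-4. The treatment effect is identical in all three cases.

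**4. Real onset at session 5, no delay, 20 per arm, one threshold.** First flagged session, % of trials:

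| Effect and rule | Before 5 | At 5 | After 5 | Never |
|---|---|---|---|---|
| 1.0 SD, unadjusted | 9-15 | 75-81 | 6-10 | 0-3 |
| 1.0 SD, Holm over 20 | 1-2 | 51-53 | 14-34 | 13-34 |
| 0.5 SD, unadjusted | 10-16 | 26-29 | 16-35 | 21-46 |
| 0.5 SD, Holm over 20 | – | 6-7 | – | 76-87 |

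Single-session power (exact t) is 0.87 at 1.0 SD and 0.34 at 0.5 SD.

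**The case against.** The strongest reply is that the sessional comparison is sound. GA is randomised and measured at every session, so GB-GA at session k removes natural recovery, conventional therapy and repeat-measurement effects, and later sessions cannot influence an earlier reading. This stands. A reader might infer that session number is confounded with time in general and that the sessional contrasts are invalid; the documents do not support that. What GA cannot remove, because it receives no LF-rTMS, is a lag between stimulation and its effect.

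The documents posit no lag; the background speaks of a direct effect on the lesional hemisphere. With no lag and good power, the first flagged session can equal the minimum on this schedule, as the 75-81% in step 4 shows. It would therefore be wrong to infer that the picked session will usually be too late. Any such percentage would come entirely from an assumed delay. The design leaves the question open; it does not show that a delay exists.

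A reader might also infer that the plan promises a lasting effect after a short course. It does not: its target is a change in excitability relative to conventional therapy. The absence of any reading after early stopping therefore counts only against the word recommended.

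Finally, the first-p<0.05 rule is inferred, and the plan also looks at change from the previous session. That limits steps 2 to 4 to one reading. Step 1 applies to any rule based on these readings.

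**Conclusion.** The concern holds in a limited form. The trial can describe when a GB-GA difference in cAMT or iAMT appears during a ten-session daily course. It cannot, by itself, establish the fewest sessions needed, because no shorter course is tested and a lag cannot be excluded. That part rests on the design alone and needs no assumed figures.

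The selection problem is conditional on the first-p<0.05 reading and on assumed effects and correlations. Under those, a false flag somewhere in the course occurs in about 13-31% of null trials on one threshold and 22-52% on both, and the median flagged session moves from about 6 to 3-4 as the arms grow from 20 to 80. Purpose 1 and the GB-GA contrast at each session are unaffected. What goes too far is presenting the flagged session as a recommended minimum.

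**What to change.** 1. Restate the second purpose as describing the time course of the GB-GA difference in cAMT and iAMT during a ten-session daily course.
2. Report the estimated difference with a confidence interval at each session.
3. Name a first session with a difference only under a multiplicity-controlled rule over ten sessions and two thresholds, for example Holm over the 20 tests. Add the session-to-session change tests to that family if they may pick the session.
4. State that no shorter course was tested, and do not call that session a recommended minimum course length.

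The text is written in the past tense. If the trial is complete, leave the objectives as written, give items 2 to 4 in the report as a limit on interpretation, and label the adjusted results post hoc.

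**Cost.** No change to data collection. The sponsor gives up a course-length recommendation. Holm also costs power: with an assumed undelayed onset at session 5, the chance of flagging that session on one threshold falls from 75-81% to 51-53% at 1.0 SD, and from about 26-29% to 6-7% at 0.5 SD. No session is flagged in 13-34% and 76-87% of trials respectively. Holm controls false early flags; it does not resolve a possible lag, so item 4 is needed whichever rule is used.

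### The plan says it will determine a maximum number of LF-rTMS sessions before a plateau, but every patient stops at session 10, so that maximum may lie outside the data even when sessional change is shown

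*Combined protocol and SAP*

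**What the plan says.** Under Statement of the Problem, the maximum is the number of "sessions that can induce significant cortical excitability changes before reaching a plateau". Purpose of the study then makes it an aim: "To determine the recommended minimum and maximum number of contralesional low frequency repetitive transcranial magnetic stimulation sessions", by analysing the sequential rate of change in cortical excitability.

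The second bullet under Null Hypothesis reads "There is no change in the sessional values of cortical excitability in response to contralesional low frequency repetitive transcranial magnetic stimulation (LF-rTMS", and continues "thus the recommended minimum and maximum number of LF-rTMS sessions that can show significant changes in cortical excitability cannot be determined". No other obstacle to finding either number is named.

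Delimitations sets one schedule: "The treatment sessions for all patients in both groups was conducted daily, five times per week for two consecutive weeks". Under Data Analysis and Statistical Design, B- Inferential statistics, the sequential rate of change is described "over the 10 therapeutic sessions were assessed by comparing the CAMT and the IAMT mean values of each session" with the session before it. Sessional values and sessional rates of change are then compared between GA and GB by t test at alpha 0.05.

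The text contains no longer course, no threshold measurement after the course, no criterion for a plateau, and no rule for what to report if none is seen.

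**The concern.** One null hypothesis is being asked to serve two questions. Rejecting *no change* is evidence relevant to a minimum. It says nothing about whether change has ended, which is what a maximum defined by a plateau requires. If the GB-GA difference in contralesional or ipsilesional active motor threshold (cAMT, iAMT) is still growing at session 10, the null is false and may well be rejected, yet the session at which growth stops has not been observed.

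The planned comparison of each session with the previous one does not close the gap, because a single step may be too small to detect while growth continues. A recommended maximum is a result that readers may act on. Without a rule, the number reported could come from where the course ended or from where a small step missed significance.

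**Working it through.** **1. The plan's own figure.** Five sessions per week x two weeks = 10 sessions (Delimitations). This matches the 10 sessions in B- Inferential statistics.

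**2. What 10 sessions can identify.** Let the mean GB-GA difference after session s be D(s) = c x min(s, m)/10: linear growth to a plateau at session m, where c is the difference at session 10.

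- For m = 10, 15 or 30 and every s from 0 to 10, min(s, m) = s, so D(s) = c x s/10 in all three cases.
- The final differences would be c, 1.5c and 3c.
- The three curves are identical over the observed range, so no test and no sample size can separate them on these data alone.
- For m = 6 the curve is flat from session 6, and the plateau lies inside the data.

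This step needs no assumed effect size.

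**3. Whether a non-significant step shows a plateau.** From the documents: 40 patients in two equal groups, so 20 per group; alpha 0.05. The plan calls the test both paired and for independent samples. I take the independent-samples form, because GA is compared with GB, and two-sided testing. Assumed, because the documents give none of these: SD 1 at each session, within-patient correlation r of 0.5, 0.8 or 0.9 between any two sessions, and a GB-GA difference at session 10 of 0.8, 1.2 or 1.6 SD, built up linearly and still rising.

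- SD of a within-patient change = sqrt(2(1 - r)).
- SE of the between-group difference in change = SD x sqrt(2/20).
- Approximate power = Phi(d/SE - 1.96), with d = c for session 10 against baseline and d = c/10 for the step from session 9 to 10. This counts only rejections in the right direction.

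Example, r = 0.8 and c = 1.2: SD = sqrt(0.4) = 0.632; SE = 0.632 x 0.316 = 0.20. The overall change is 1.2/0.20 = 6.0 SE, power about 1.00. The last step is 0.12/0.20 = 0.6 SE, power Phi(-1.36) = 0.087.

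| r | c | Overall: formula / simulated | Step 9 to 10, still rising: formula / simulated | Step 9 to 10, true plateau at 6: simulated |
|---|---|---|---|---|
| 0.5 | 0.8 | 0.716 / 0.703 | 0.044 / 0.060 | 0.051 |
| 0.8 | 1.2 | 1.00 / 1.00 | 0.087 / 0.084 | 0.055 |
| 0.9 | 1.6 | 1.00 / 1.00 | 0.204 / 0.197 | 0.043 |

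The simulation used 3,000 replicates per scenario. Over all nine combinations with a rising effect, the overall comparison rejects in 70% to 100% of trials and the last step in about 6% to 20%. With a true plateau at session 6, the last step is significant in about 4% to 6%. A non-significant last step is therefore the usual result in both cases and does not distinguish them.

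**The case against.** **The null does not say that change makes both numbers determinable.** It says only that without change neither can be determined, which is correct. This stands as a reading of the words. But the statement is set up to be rejected, the purpose is to determine both numbers, and no further condition for the maximum appears anywhere. The gap lies in the purpose and the analysis taken together.

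**A plateau may occur before session 10.** If so, the maximum is observable, and it would be wrong to say that this design can never find one. What is missing is a criterion for recognising a plateau and a provision for the other case.

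**Recovery without LF-rTMS.** A reader might infer that change within GB alone, from recovery or conventional therapy, would reject the null. The documents do not support that. The null concerns change in response to LF-rTMS, thresholds are measured each session in both groups, and the sessional comparison is GB against GA.

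**A report of 10.** A reader might also infer that the plan would report exactly 10 as the maximum. No passage says so. By the plan's own definition, an effect with no plateau has no maximum to report, and step-by-step testing could as easily suggest a false early plateau.

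**Reach.** The first null hypothesis, the randomised pre-to-post comparison and the motor outcomes are unaffected. That limits the seriousness but leaves the second purpose unsupported.

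**Conclusion.** The point holds for the maximum. The second purpose promises a number that the design can deliver only if the GB-GA difference levels off within 10 sessions, and the plan provides neither a way to show levelling-off nor a way to report its absence. The censoring argument is logical and rests only on the fixed 10-session course. The statement that a non-significant step is weak evidence of a plateau is general; the 6% to 20% figures rest on the assumed SD, correlations, effect sizes and linear growth, and are illustrative.

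The documents do not allow the size of the problem to be estimated. A reader might try to size it from an assumed build-up curve, such as an exponential approach to a plateau, but neither the curve nor its rate is in the plan, so the result would only restate the assumption. The wording should be changed, because the change alters what the trial may conclude.

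**What to change.** 1. **Purpose of the study, second bullet:** add that both numbers are sought *within a course of 10 sessions*.
2. **Null Hypothesis, second bullet:** keep the statement about sessional change, worded as the GB-GA contrast that the analysis already uses, and remove the maximum from it.
3. **B- Inferential statistics:** add a rule for the maximum. A maximum at session k is reported only if the confidence interval for the further change in the GB-GA difference from session k to session 10 lies within a margin fixed before analysis. Otherwise the conclusion is *no plateau shown within 10 sessions; maximum not determined*. State the margin, the confidence level, whether the rule applies to cAMT, iAMT or both, the order in which values of k are examined, and the latest k that may be claimed. The last item matters because a single step of steady growth is small (0.12 SD in the example above) and could fit inside a margin while growth continues.

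**Cost.** Wording and one added analysis; no new data. The downside is that the trial may have to report the maximum as not determined. Under the SEs assumed above, a 95% interval has half-width 1.96 x SE: 1.96 x 0.316 = 0.62 SD for r = 0.5, 1.96 x 0.20 = 0.39 SD for r = 0.8, and 1.96 x 0.141 = 0.28 SD for r = 0.9. A narrower margin could not be met even if the estimated further change were zero. The text is written in the past tense; if the sessional data have already been examined, the margin should be labelled post hoc.

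This concerns inference only and says nothing about how many sessions should be given.
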